6.15.2. Safety Subgroup Analysis

Safety subgroup analysis for common TEAEs may be summarized by treatment and overall, for the safety population during the Induction and Maintenance Periods.

6.16. Protocol Violations

Review of all major and minor protocol violations will be performed on an ongoing basis during the conduct of the study. All protocol exemptions/violations identified from the following sources will be tracked:

- During clinical monitoring visits
- During data validation process

No patient will be excluded from the ITT population due to any protocol violations.

There is no Per-Protocol Population in this plan.

All protocol exemptions and violations that require medical review will be listed.

For the purpose of protocol deviation programming for prior medications the following imputation will be applied.

If month and day are both missing, impute to Jan 1; and if day is missing, impute to 1.

When year, month and day are missing the date will be treated as missing (i.e. there will be no imputations).

This imputation will be applied for partial end dates alone and will only be used for protocol deviation programmable purposes. Since many of the important protocol deviation categories identify certain medications within weeks of baseline, the end dates of prior meds are imputed as described above. Table 9 lists the categories, subcategories, and study specific terms of important protocol deviations.

Table 9 Description of Important Protocol Deviations

Category / Subcategory / Study_specific	Source	Methods of Identification	Comment

Category: Informed Consent			
Subcategory:			
Informed Consent Not Obtained	Non Programmable (Monitoring)	202 = Procedure done prior to obtaining ICF	
Improper Consent	Non Programmable (Monitoring)	201 = Improper administration of ICF	
Improper Consent	Non Programmable (Monitoring)	203 = Incorrect ICF version used	
Category: Eligibility			
Subcategory: Inclusion / Exclusion			
Study_specific:			
Inclusion/Exclusion	Non Programmable (Monitoring)	105 = Violation of inclusion/ exclusion criteria	
Age < 18 or > 75 years of age at the time of initial Screening	Programmable (clinical database)		Use informed consent date (this is the same as initial screening).
Have a Mayo score < 6 or > 12 (during screening*), with an endoscopic subscore < 2 in first 14 days prior to first dose of study treatment	Non Programmable (Monitoring)		Mayo is full Mayo (inclusive of PGA subscore).
Have Anti-TNF therapy within 8 weeks of baseline*	Programmable (clinical database)		As defined in section 6.15.1 of the SAP. ATC code=L04AB
Have Vedolizimab treatment within 12 weeks of baseline*	Programmable (clinical database)		Preferred_Name='VEDOLIZUMAB' and ATC code=L04AA
5-ASA compound dosing has not been stable < 2 weeks before screening*	Non Programmable (Monitoring)		ATC Code: A07EC Stable = dose level not changed.
Thiopurine prescribed dose is not stable < 8 weeks before baseline*	Programmable (clinical database)		As defined in section 6.15.1 of the SAP. Preferred name="AZATHIOPRINE" AND ATC codes L04AX, L01BB

Have hematologic absolute neutrophil count < 1.5 x 10 ⁹ /L at screening*	Programmable (clinical database)		Lbtest=' Neutrophils, Segmented'. Last lab collected on or before date of randomization will be utilized.
Have hematologic platelet count <100x10 ⁹ /L at screening*	Programmable (clinical database)		Lbtest=' Platelets'. Last lab collected on or before date of randomization will be utilized.
Have hematologic hemoglobin level <10.0g/dL at screening*	Programmable (clinical database)		Lbtest=' Hemoglobin' (note the unit was g/L in LB) . Last lab collected on or before date of randomization will be utilized.
Have hematologic lymphocyte count ≤500 cells/μL at screening*	Programmable (clinical database)		Lbtest=' Lymphocytes' (note the unit was 10 ⁹ /L in LB) . Last lab collected on or before date of randomization will be utilized.
Have hematologic total white blood cell count <3.0 x 10 ⁹ /L at screening*	Programmable (clinical database)		Leukocytes to be used for calculation of WBC count. . Last lab collected on or before date of randomization will be utilized.
Have chemistry: serum creatinine levels >2x upper limit of normal (ULN) at screening*	Programmable (clinical database)		May need to alter the ULN based on volume of subjects violating. LBTEST=' Creatinine'. Last lab collected on or before date of randomization will be utilized.
Have chemistry: total bilirubin level >2x upper limit of normal (ULN) at screening*	Programmable (clinical database)		May need to alter the ULN based on volume of subjects violating. LBTEST=' Bilirubin'. Last lab collected on or before date of randomization will be utilized.
Have chemistry: alkaline phosphatase >2x upper limit of normal (ULN) at screening*	Programmable (clinical database)		May need to alter the ULN based on volume of subjects violating. LBTEST=' Alkaline Phosphatase'. Last lab collected on or before date of randomization will be utilized.
Have chemistry: alanine aminotransferase (ALT) levels >2x upper limit of normal (ULN) at screening*	Programmable (clinical database)		May need to alter the ULN based on volume of subjects violating. LBTEST=' Alanine Aminotransferase'. Last lab collected on or before date of randomization will be utilized.

Have chemistry: aspartate aminotransferase (AST) levels >2x upper limit of normal (ULN) at screening*	Programmable (clinical database)		May need to alter the ULN based on volume of subjects violating. LBTEST=' Aspartate Aminotransferase'. Last lab collected on or before date of randomization will be utilized.
Have received cyclosporine or thalidomide ≤30 days of screening* for treatment of UC.	Programmable (clinical database)		Use Preferred name="CICLOSPORIN" or "TACROLIMUS" when ATC Codes L04AD or Preferred name="THALIDOMIDE" when ATC code=L04AX.
Have received corticosteroid enemas, corticosteroid suppositories or topical treatment with 5-ASA ≤30 days of screening* endoscopy for treatment of UC.	Non Programmable (Monitoring)		
Have used apheresis (Adacolumn apheresis) ≤2 weeks before screening* endoscopy for treatment of UC.	Programmable (clinical database)		Use Preferred name="MEDICAL DEVICES".
Have previous exposure to any biologic therapy for IL-23 (ustekinumab), either licensed or investigational.	Programmable (clinical database)		Preferred_Name='USTEKINU MAB'.
Have abdominal abscess or toxic megacolon during screening*	Non Programmable (Monitoring)		
Have positive hepatitis B surface antigen or positive anti-hepatitis B core antibody (HBcAb+) and positive confirmatory polymerase chain reaction (PCR) for HBV, regardless of anti-hepatitis B surface antibody status at screening*	Programmable (clinical database)		'Hepatitis B Virus Surface Antigen' 'Hepatitis B Virus Core Antibody'

Have positive result for hepatitis C antibody and positive confirmatory PCR test for hepatitis C virus at screening*	Programmable (clinical database)		'Hepatitis C Virus Antibody'
Had Clostridium difficile within 30 days of screening endoscopy or tests positive at screening*	Programmable (clinical database)		

* For definition of Baseline and Screening, Date of Randomization should be used for consistency throughout.

Category: Investigational Product			
Subcategory:			
Treatment Assignment/ Randomization Error			
Dosing Error	Non Programmable (Monitoring)	104 = Study drug not administered per protocol	
Compliance	Programmable (clinical database)	Patient received a dose adjustment but was not eligible for a dose adjustment per protocol.	Only patients in the 50 mg and 200 mg induction treatment arms are eligible for adjustment.
Compliance	Programmable (clinical database)	Patient experienced a TDM dose decrease.	Protocol specified that patients will not experience a dose decrease on the basis of drug concentrations (protocol section 9.5).
Compliance (Missed Dose)	Programmable (clinical database)	Dose missed or administered outside of the protocol defined visit window.	Out of window is defined as +/- 14 days.
Category: Study Procedures			
Subcategory:			
Excluded Conmeds	Non Programmable (Monitoring)	103 = Excluded Medication Used	
Visit Schedule Criteria	Non Programmable (Monitoring)	101 = Visit/ Procedure out of window	

Other	Non Programmable (Monitoring)	102 = Visit/ Procedure not done	
Category: Other			
Subcategory:			
Other	Non Programmable (Monitoring)	106 = Other protocol deviation	
Other	Non Programmable (Monitoring)	208 = Other regulatory deviation	
Category: Administrative/Oversight			
Subcategory:			
Improper Conduct of Assessments	Non Programmable (Monitoring)	207 = Procedure performed by non-delegated personnel	
Reg/Ethic Approvals	Non Programmable (Monitoring)	204 = IRB approval not obtained prior to screening	
Reg/Ethic Approvals	Non Programmable (Monitoring)	205 = IRB approval expired	
Category: Safety			
Subcategory:			
SAEs	Non Programmable (Monitoring)	206 = Failure/delay in SAE reporting	

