8.1. Inclusion Criteria

Subjects with UC are eligible for enrollment only if they meet all of the following criteria during screening:

- [1] have given written informed consent approved by the ERB (ethical review board) governing the site
- [2] are male or female subjects ≥ 18 and ≤ 75 years of age at the time of initial screening
 - [2a] male subjects agree to use a reliable method of birth control during the study and for 3 months, which is greater than 5 half-lives, after the last dose of investigational product
 - [2b] female subjects:
 - are women of childbearing potential whose serum pregnancy test results are negative and who agree to use a reliable method of birth control (eg, condom, sponge, or diaphragm combined with spermicidal foam, gel, or cream; ongoing hormonal contraception [oral, intramuscular, depot, or transdermal], such as Depo-Provera, Evra, or NuvaRing; an intrauterine device; or complete abstinence from sexual intercourse with men) during the study and for 3 months after the last dose of the investigational product

-or-

- are not women of childbearing potential, defined as having:
 - bilateral oophorectomy, tubal ligation, or hysterectomy at least 6 weeks before screening;
 - spontaneous amenorrhea for ≥ 12 months, not induced by a medical condition or medications; or
 - spontaneous amenorrhea for 6 to 12 months and a follicle-stimulating hormone level greater than 40 mIU/mL at screening
- [3] venous access sufficient to allow blood sampling and IV administration (if applicable), as per the protocol
- [4] have had a diagnosis of UC for ≥ 3 months before baseline (endoscopic evidence corroborated by a histopathology report); a biopsy for a local histopathology evaluation (to obtain a report) can be obtained during the baseline endoscopy procedure if a histopathology report is not available
- [5] have moderate to severe active UC as defined by a Mayo score of 6 to 12 with an endoscopic subscore ≥ 2 within 14 days before the first dose of study treatment (note: a partial Mayo score of at least 4 and other eligibility criteria must have been met before endoscopy is performed as a study procedure)
- [6] have evidence of UC extending proximal to the rectum (≥ 15 cm of involved colon)

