- [7] have documentation of a surveillance colonoscopy (performed according to local standard) within 12 months before baseline (may be performed during screening) for subjects with pancolitis of >8 years' duration or left-sided colitis of >12 years' duration
- [7a] up-to-date colorectal cancer surveillance (performed according to local standard), for subjects with family history of colorectal cancer, personal history of increased colorectal cancer risk, age >50 years, or other known risk factor
- [8] subjects must either:
 - [8a] be naive to biologic therapy (such as TNF antagonists, vedolizumab, or experimental UC biologics) and have at least 1 of the following:
 - inadequate response or failure to tolerate current treatment with oral or IV corticosteroids or immunomodulators (6-MP or AZA) or
 - history of corticosteroid dependence (an inability to successfully taper corticosteroids without return of UC)

OR

- [8b] have also received treatment with 1 or more biologic agents (such as TNF antagonists, vedolizumab, or experimental UC biologics) with or without documented history of failure to respond or tolerate such treatment

- the biologic treatment must have been discontinued according to the following timelines:
 - anti-TNF therapy at least 8 weeks before baseline
 - vedolizumab treatment at least 12 weeks before baseline
 - experimental biologic UC therapy at least 8 weeks before baseline
- [9] may be receiving a therapeutic dosage of the following drugs:
- [9a] oral 5-ASA compounds: if the prescribed dose has been stable for at least 2 weeks before screening endoscopy
- [9b] oral corticosteroid therapy (prednisone ≤ 20 mg/d or equivalent): if the prescribed dose has been stable for at least the 2 weeks before screening endoscopy
- [9c] AZA or 6-MP: if the prescribed dose has been stable for at least 8 weeks before baseline
- [10] are willing and able to complete the scheduled study assessments, including endoscopy
- [11] have clinically acceptable laboratory results at screening, as assessed by the investigator, including:
- [11a] hematologic: absolute neutrophil count $\geq 1.5 \times 10^9/L$, platelet count $\geq 100 \times 10^9/L$, hemoglobin level ≥ 10.0 g/dL, lymphocyte count > 500 cells/ μL , and total white blood cell count $\geq 3.0 \times 10^9/L$

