8.2. Exclusion Criteria

Subjects will be excluded from study enrollment if they meet any of the following criteria:

- [12] have been diagnosed with indeterminate colitis, proctitis (distal disease involving the rectum only; less than 15 cm from the anal verge) or CD
- [13] have had surgery for treatment of UC or are likely to require surgery for UC during the study
- [14] have received any of the following for treatment of UC:
- [14a] cyclosporine or thalidomide within 30 days of screening endoscopy
- [14b] corticosteroid enemas, corticosteroid suppositories, or topical treatment with 5-ASA within 30 days of screening endoscopy
- [14c] have used apheresis (eg, Adacolumn apheresis) ≤ 2 weeks before screening endoscopy

- [15] have previous exposure to any biologic therapy targeting IL-23 (including ustekinumab), either licensed or investigational
- [16] have been treated with any investigational drug for UC within 30 days or 5 half-lives of the drug (whichever is longer) before the initial screening visit (Visit 1), OR with interferon therapy within 8 weeks before baseline
- [17] have evidence of abdominal abscess or toxic megacolon during screening
- [18] have extensive colonic resection, subtotal or total colectomy, ileostomy, colostomy, or fixed symptomatic stenosis of the intestine
- [19] have evidence of active or latent TB (refer to Section 10.3.2.2 for details on full TB exclusion criteria)
- [20] have had any malignancy within 5 years of screening, except for basal cell or squamous epithelial carcinoma of the skin that has been resected with no evidence of metastatic disease for at least 3 years OR cervical carcinoma in situ with no evidence of recurrence within 5 years of screening
- [21] are investigator site personnel directly affiliated with this study and/or their immediate families. Immediate family is defined as a spouse, parent, child, or sibling, whether biological or legally adopted
- [22] are Lilly employees or employees of third-party organizations (TPOs) involved with the study
- [23] are currently enrolled in a clinical trial involving an investigational product or nonapproved use of a drug or device, OR are concurrently enrolled in any other type of medical research not scientifically or medically compatible with this study, per investigator judgment
- [24] have previously completed or withdrawn from this study or any other study investigating LY3074828. This criterion does not apply to subjects undergoing rescreening procedures

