Note: The Mayo score ranges from 0 to 12, with higher scores indicating more severe disease. Partial Mayo score excludes endoscopy and ranges from 0 to 9.

Adapted from: Schroeder KW, Tremaine WJ, Ilstrup DM. Coated oral 5-aminosalicylic acid therapy for mildly to moderately active ulcerative colitis. A randomized study. *N Engl J Med.* 1987;317(26):1625-1629.

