6.8. Patient Characteristics

The patient's year of birth, sex, weight, height, smoking habits, previous biologic treatment, and other demographic characteristics are collected at the screening visit. Age and body mass index will be calculated.

Only the year of birth is collected at screening. For the purpose of age calculation, the month and day of birth will be imputed as July 01, of the year of birth. Age is computed as follows;

$$\text{Age} = (\text{Informed Consent Date} - \text{Date of Birth} + 1) / 365.25.$$

Demographic and baseline characteristics (including age, gender, race and ethnicity) will be summarized for each treatment group.

Certain characteristics, that are collected at baseline or after baseline but not summarized in the demographic summary, will be reported as a listing.

No inferential analysis for the comparability of baseline covariates across treatment groups will be performed.

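### Several eligibility rows in SAP Table 9 do not match the protocol criteria they stand for, so the important-deviation listing would be wrong if they are followed literally

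*SAP*

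**What the plan says.** Five rows in the Eligibility part of SAP Table 9 are set here against the protocol.

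- **Disease activity.** Protocol 8.1, criterion [5]: "have moderate to severe active UC as defined by a Mayo score of 6 to 12", together with an endoscopic subscore of at least 2, within 14 days before first dose. Table 9: "Have a Mayo score < 6 or > 12 (during screening*), with an endoscopic subscore < 2 in first 14 days". The row's source is monitoring, not programming.
- **Thiopurines.** Criterion [9c]: "AZA or 6-MP: if the prescribed dose has been stable for at least 8 weeks before baseline". Table 9 (programmable) refers to SAP 6.15.1 and then specifies "Preferred name='AZATHIOPRINE' AND ATC codes L04AX, L01BB". In 6.15.1 the azathioprine name restriction is attached to L04AX only; L01BB is taken whole.
- **IL-23 exposure.** Criterion [15] excludes patients who "have previous exposure to any biologic therapy targeting IL-23 (including ustekinumab), either licensed or investigational". The Table 9 program searches for one preferred name, ustekinumab.
- **Cyclosporine/thalidomide.** Criterion [14a] names these two drugs. The Table 9 search also selects tacrolimus.
- **Age.** Criterion [2] allows 18 to 75 years inclusive at initial screening. Table 9 flags below 18 or above 75, programmed with the consent date. SAP 6.8 says only year of birth is collected, that "the month and day of birth will be imputed as July 01", and that age is a day difference divided by 365.25. It gives no truncation rule.

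Three other statements bear on the consequences. Table 9 opens its eligibility section with a general monitoring row, code 105, for any inclusion or exclusion violation. SAP 6.16 removes no one from ITT for a violation and states that the plan has no Per-Protocol population. SAP 6.2 says a Per-Protocol population may be evaluated, and that a sensitivity analysis of the primary analysis may exclude major deviations.

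**The concern.** A deviation check should be the logical negation of its criterion, applied to data that can support it. Where a criterion needs two conditions, failing either is a violation. Where it covers a class of drugs, the search has to cover the class. Where it depends on a birthday, a birth year cannot settle the boundary cases.

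The disease-activity row matters most. Under protocol 10.1.1, remission requires an endoscopy subscore of 0 or 1. A patient randomised with a subscore of 1 and a Mayo score of 6 or more already meets that component at baseline, and the row's literal wording does not describe that patient as a deviation.

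At stake are the accuracy of the important-deviation listing and the content of any sensitivity analysis that draws on it.

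**Working it through.** No figure in the plan depends on these rows, so there is nothing to reproduce. The checks are logical.

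**Disease activity.** Protocol Attachment 5 scores four items 0 to 3, giving 4 × 4 × 4 × 4 = 256 combinations. Since "The Mayo score ranges from 0 to 12", the row's upper branch can never occur. Let *s* be the sum of the three non-endoscopic items. The number of combinations for *s* = 0 to 9 is 1, 3, 6, 10, 12, 12, 10, 6, 3, 1 (total 64).

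| Endoscopy | Total < 6 | Total ≥ 6 |
|---|---|---|
| 0 | 44 (*s* ≤ 5) | 20 |
| 1 | 32 (*s* ≤ 4) | 32 |
| 2 | 20 (*s* ≤ 3) | 44 |
| 3 | 10 (*s* ≤ 2) | 54 |

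- Eligible under [5]: 44 + 54 = 98. Ineligible: 256 − 98 = 158.
- Flagged by the row read literally (both failures): 44 + 32 = 76.
- Missed: 158 − 76 = 82, made up of 20 + 32 = 52 with Mayo at least 6 and endoscopy below 2, and 20 + 10 = 30 with Mayo below 6 and endoscopy at least 2.
- Eligible combinations flagged: 0.
- With the two failures joined by OR: 0 of 158 missed and 0 of 98 eligible flagged.

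The 30 all have *s* ≤ 3. Criterion [5] also requires a partial Mayo score of at least 4 before endoscopy, so they should arise only if the partial score falls after that check. The 52 all have *s* ≥ 5 and are not screened out that way.

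**Thiopurines.** The comment requires the azathioprine name under both ATC codes, so a 6-MP record is not selected. Under the 6.15.1 definition, all of L01BB is selected. The row therefore supports two different programs.

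**IL-23.** Criterion [15] gives ustekinumab as one instance of a class. The protocol Introduction describes other agents against the p19 subunit with activity in psoriasis and Crohn's disease. Exposure to one of those would not be found by the search.

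**Tacrolimus.** A patient whose only relevant record is tacrolimus is flagged under a row that represents [14a], without having met [14a] as written.

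**Age.** Computed age = (consent date − 1 July of birth year + 1) / 365.25. Examples:

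- Born 15 Nov 1998, consent 1 Sep 2016: true age 17, computed 18.17, passes.
- Born 1 Feb 1998, consent 1 Mar 2016: true age 18, computed 17.67, flagged.
- Born 1 Feb 1941, consent 1 Sep 2016: true age 75, computed 75.17, flagged unless truncated.

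Now assume birthdays (*u*) and consent dates (*c*) are uniform over the year, on a 0–1 scale, and read the upper limit as completed years.

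- 17-year-olds who pass: born in consent year − 18, *u* > *c*, *c* > ½. The integral of (1 − *c*) from ½ to 1 is 1/8.
- 18-year-olds flagged: same birth year, *u* ≤ *c*, *c* < ½. The integral of *c* from 0 to ½ is 1/8.
- 75-year-olds flagged, age untruncated: birth year − 75 contributes the integral of *c* from ½ to 1, which is 3/8. Birth year − 76 contributes all of its 75-year-olds, 1/2. The sum is 7/8.

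A day-by-day enumeration for 2016 agrees. In birth year − 18, 12.6% wrongly pass and 12.4% are wrongly flagged. Untruncated, about 50% of each of birth years − 75 and − 76 are eligible but flagged; the first 50% is 3/8 aged 75 plus 1/8 aged 74. If computed age is truncated, birth year − 75 has no errors, and birth year − 76 has 12.6% wrongly flagged and 12.4% wrongly passed.

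**The case against.** The best defence is that the disease-activity row is a label for a monitor, not code. The monitor works from criterion [5], and the row's connecting word copies the protocol's own phrase, "Mayo score of 6 to 12 with an endoscopic subscore". Code 105 sits above it as a catch-all. The thiopurine row cites 6.15.1, which would bring 6-MP in. The age row does not cite 6.8, so a truncated age is possible. And nobody leaves ITT.

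Most of this stands as a limit on the consequences. A reader might infer that ineligible patients escape the deviation list; the documents do not show that, because code 105 can record any eligibility violation found at monitoring. A reader might infer that 6-MP users are certainly unchecked; that follows from one reading of an ambiguous cell. A reader might infer that all these rows also flag eligible patients; on the points raised here, the disease-activity, thiopurine and IL-23 rows only under-detect.

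What does not stand is the inference that the rows can be left alone. Table 9 is the written specification. Three of the mismatched searches are programmable, and a monitoring code does not correct a program that selects the wrong records. A row that conflicts with its own cross-reference needs one rule.

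**Conclusion.** The rows should be corrected; the effect is confined to secondary outputs. Under-detection applies to the disease-activity, thiopurine and IL-23 rows. Over-flagging applies only to the age and tacrolimus items, and the age row can also miss 17-year-olds. The age wording itself negates criterion [2]; the fault lies in the year-only birth date and the missing truncation rule.

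The 82 of 158 counts score combinations on a literal reading and is not an expected share of patients. The one-eighth figures assume uniform dates. The seven-eighths figure assumes, in addition, that age is not truncated and that the upper limit means completed years. Only patients in boundary birth years are affected, and the documents give no count of them, nor of 6-MP users or patients exposed to other IL-23 agents.

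A reader might infer that the primary result is at risk. It is not: the primary analysis is ITT and no violation removes a patient. Nor can an effect on a Per-Protocol analysis be asserted, because 6.16 says there is none while 6.2 allows one. The sensitivity analysis in 6.2 is optional and turns on deviations judged major, and the SAP does not say whether those are the important deviations of Table 9.

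**What to change.** Amend Table 9 as follows.

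- **Disease activity:** full Mayo below 6, OR endoscopic subscore below 2, OR not assessed within 14 days before first dose. Drop the impossible upper branch and keep the 14-day window.
- **Thiopurines:** any L01BB, or L04AX with preferred name azathioprine, as in 6.15.1.
- **IL-23:** a medically reviewed list of all IL-23-targeting biologics, licensed or investigational, including ustekinumab.
- **Cyclosporine/thalidomide:** reconcile the search with [14a] on tacrolimus.
- **Age:** program only certain violations, where consent year minus birth year is below 18 or above 76. For differences of exactly 18 or 76, use the site's inclusion/exclusion record.

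Also reconcile 6.2 with 6.16 on the Per-Protocol population. The cost is table wording and light reprogramming, with no new data collection.
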